- Does participation in the TRAC intervention lead to improvements in medication adherence?

- Does participation in the TRAC intervention impact other clinical HIV outcomes, including CD4 count and viral load?

3. Study Objectives

The aim of the study is to conduct a pilot randomized controlled trial of the TRAC intervention among PLWHA:

- Two-month, randomized-controlled waitlist trial with 2-month follow-up ($N=50$)
- Feasibility evaluation, focusing on recruitment, engagement, and adherence
- Evaluation of effects on overall alcohol consumption, HAART adherence, and clinical outcomes

4. Study Design

Description of relevance to the VA

HIV occurs among veterans at a higher rate than among those in the general population. Moreover, many veterans struggle with alcohol use disorders, which can impact their health and overall quality of life. The TRAC intervention, which aims to reduce alcohol use among people living with HIV/AIDS, thus meets two important needs among the VA patient population.

Study Population and patient selection

Subject Inclusion Criteria: To be eligible to participate in the intervention, patients must be 1) HIV-positive, 2) 18 years and older, 3) an at-risk drinker as identified through a screening procedure, 4) currently taking HIV medication and 5) a patient receiving care at one of the study recruitment sites. Based on NIAAA's screening recommendations, every person living with HIV who reports to participating clinics will complete a short screening procedure. Clinical data of interest including alcohol dependency diagnoses and prescription use will be pulled from CDW via VINCI, CCR and HAVACS. These clinical indicators will be used to create a list of eligible patients with appointments in the coming month for screening. The list of eligible patients will be stored in the secure VINCI project folder and then downloaded to the secure local VA drive for use by study coordinators. The only two locations in which the list will be stored are within VINCI and on the secure local drive. After a list of patients has been created, the study coordinator will screen the patient EMR (CPRS/VISTA) for inclusion criteria.

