2. Upon arrival to the clinic for the first intervention session, the patients will be shown to a private room to begin their first videoconferencing session
3. The patient will be given a laptop to complete the initial assessment battery
4. If the participant is in need of a study phone, the VA coordinator will provide this phone, along with the breathalyzer, to the participant
5. Participants will begin the first intervention session, which will consist of the following content/tasks:
 - a. Introductions and orientation to the technology (smartphone and breathalyzer, stored at the clinic; tutorial handouts provided)
 - b. Review of self-monitoring procedures and setting of "do not disturb" hours
 - c. Review of breathing awareness exercise
 - d. Scheduling follow-up intervention sessions for weeks 2-8, conducted via mobile phone
 - e. A short post-session satisfaction survey, delivered via text message and completed immediately following the session.
6. The day after the first session, participants will begin self-monitoring their alcohol, medication use, and mental health
 - a. They will be texted at two random times each day using an automated software to complete a breathalyzer reading and finish a survey
 - b. If participants do not respond to the request within 30 minutes, a text reminder will be sent, followed by another an hour later.
 - i. If the participant is in a situation where they are unable to complete the breathalyzer test, they will be able to respond to the text message and request a follow-up reminder two hours later.
 - c. If participants wish to go to sleep for the night and have not yet received their evening reminder, they can elect to complete a breathalyzer reading and survey before going to bed.
 - d. Self-monitoring will continue through the end of week 8 (until they return to the VA to complete their post-test and return their equipment)
 - e. Participants will be instructed to call the interventionist if they have any technical difficulties throughout the course of the study
7. Sessions 2-8 of the intervention will be conducted via phone call, with patients instructed to find a private room at home from which to speak with their counselor.
 - a. After each session, the participant will complete a short post-session satisfaction survey, delivered via text message and completed immediately following the session

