In the event that identifying information is released to an unauthorized party, the serostatus of participants could be revealed to unwanted individuals. This could potentially cause harm, but is unlikely considering the careful plans in place regarding data management and protection. All possible measures will be taken to protect information provided through surveys, interviews, and intervention participation, and confidentiality will be respected. Following completion of data collection, responses will become anonymous as identifying information is permanently deleted. For these reasons, we estimate that this minimally-invasive project poses minimal risk.

STATISTICAL ANALYSIS PLAN

For the randomized controlled trial, data analytic methods will be focused on examining acceptability and feasibility, as well as effects on alcohol intake, HAART adherence, and HIV-related medical outcomes (CD4 count and viral load). Intervention adherence, daily monitoring adherence, and session acceptability will be described using descriptive statistics. Session attitudes will be assessed using several 5-point semantic differential attitudinal measures rating the session, including Boring/Interesting, Unpleasant/Pleasant, Bad/Good, Useless/Useful, and Negative/Positive. Scores on the session attitude semantic differential measures will be reverse-coded where required and averaged to form an overall attitude score, with “0” being “neutral.”

We will provide descriptive summaries for the outcome variables, including mean, median, and standard deviation for continuous variables and counts and percentages for categorical variables. We will summarize the outcome variables overall and across the intervention groups. In assessing the differences in alcohol use and medication adherence between the two groups during the 8-week intervention period, we will utilize the Kruskal–Walli’s test, a non-parametric statistical approach, to compare the distribution of outcome variables. The general linear model (ANOVA) will be used to estimate the difference between alcohol use and medication adherence among the groups, and the estimation of the effect size (Cohen’s D) at the end of the 8-week intervention period. While this study was not powered to detect significant differences, the goal of these analyses is to observe changes and effect sizes that may provide preliminary evidence of efficacy.

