To examine intervention effects as assessed through daily surveys, we will examine responses to the morning survey question asking if participants had consumed alcohol on the previous day (yes/no), whether or not they reported a positive breathalyzer reading (> 0.0), and if they had taken all of their HAART on the previous day (yes/no). Within the 8-week intervention period and using the daily data, we will assess the change in the proportion of participant's alcohol use, the proportion of positive breathalyzer readings, and the proportion of their medication use from the beginning of week 1 to the end of week 8 using McNemar's matched pair test. This test will allow us to address the interdependency in the repeated measurements. We will account for missing survey responses by considering two scenarios: First, assuming they were missing completely at random and remained missing, and second, that missing values were indicative of alcohol use/medication nonadherence and were thus filled in as drinking days/positive breathalyzers/nonadherent days (a conservative approach).

All participants will have received the intervention by the end of the 8 week (2-month) post-intervention period. To examine long-term intervention effects, participants from both the waitlist-control and intervention group will be combined into a single dataset. A generalized linear model (via SAS GENMOD PROCEDURE) and a multiple linear regression model will be fit to the change from baseline for each outcome measure. Change from baseline is the difference between the baseline value and values obtained at subsequent time points: 8 weeks (immediate post-intervention; T2 for intervention group and T3 for waitlist-control), and 16 weeks (2 months post-intervention; T3 for intervention group and T4 for waitlist-control) for each outcome measure. The rationale for fitting the change from baseline is that this model removes the effect of baseline differences that may exist from the model. All statistical hypothesis tests will be conducted using the standard 5% significance level. SAS Version 9.4 (TS1M1, SAS Institute, Cary, NC), will be used for all analyses.

References

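### Filling missing daily values as drinking or nonadherent is conservative for a week-1 to week-8 change only if missingness does not weigh more heavily on week 1; the SAP states the label without that condition.

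*Combined protocol and SAP*

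**What the plan says.** The daily-survey paragraphs of the Statistical Analysis Plan take three yes/no items: drinking on the previous day, a positive breathalyzer reading, and all HIV medication taken on the previous day. Each is analysed as a change in proportion "from the beginning of week 1 to the end of week 8 using McNemar's matched pair test".

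Missing responses are handled under two scenarios. The first is "First, assuming they were missing completely at random and remained missing". The second supposes that "missing values were indicative of alcohol use/medication nonadherence and were thus filled in as drinking days/positive breathalyzers/nonadherent days (a conservative approach". The fill is not restricted to one end of the period, and no condition is attached to the description of it as conservative.

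Two further statements set the context. "All statistical hypothesis tests will be conducted using the standard 5% significance level", so these comparisons will produce p-values. The preceding part of the plan says of its between-group analyses, "While this study was not powered to detect significant differences", and gives their goal as observing changes and effect sizes. Daily-monitoring adherence will be described, but the plan does not ask for it by week or tie it to this analysis.

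**The concern.** Counting a missing value as a bad outcome is conservative for a level at one time point, such as the proportion drinking in week 8. It has no fixed direction for a change, because the fill raises the week-1 proportion too. If more is missing at the start than at the end, part of the artificial excess disappears by week 8 and looks like improvement.

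An apparent benefit that survives a scenario labelled conservative will tend to be read as robust, when it could come from a change in response rates. There is no concurrent comparison to cancel this: daily data exist only during each participant's own 8-week intervention period (section 5, Collection and record keeping).

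**Working it through.** **Inputs from the documents.** N = 50 (section 3); a within-person comparison of week 1 with week 8 by McNemar's test; 5% level; the same fill at both ends. The SAP states no missingness, event rate or effect size for this analysis, so there is no figure of its own to reproduce.

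**Assumptions.** Event rates and missing fractions are as shown in each case. In the worked cases missingness is unrelated to the outcome within a week, so q = p. Each person contributes one week-1 day and one week-8 day, because the SAP does not say how daily records form pairs. The latent within-person correlation is 0.4. Tests are two-sided.

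**Formula.** Let p be the true event rate in a week, m the fraction missing, and q the true event rate on the missing days. Filling turns the non-event missing days into events, so

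filled proportion = p + m(1 − q)

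filled change = (p8 − p1) + [m8(1 − q8) − m1(1 − q1)]

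The bracket is the bias. For an undesirable event, a negative bias favours the intervention. The fill is therefore conservative for benefit only if m8(1 − q8) ≥ m1(1 − q1).

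**Case A: drinking flat at 40%, missing 25% then 10%.**
- Week 1: 0.40 + 0.25 × 0.60 = 0.55
- Week 8: 0.40 + 0.10 × 0.60 = 0.46
- Apparent change: −9 points; true change: 0.
- Chance of a significant result in the favourable direction, by exact enumeration with 50 pairs: 16.9% with the uncorrected McNemar chi-square and 11.4% with the exact-binomial version. With no missing data the figures are 2.5% and 1.5%.

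**Case B: nonadherence flat at 10%, missing 25% then 10%.**
- Week 1: 0.10 + 0.25 × 0.90 = 0.325
- Week 8: 0.10 + 0.10 × 0.90 = 0.19
- Apparent change: −13.5 points; favourable significance 36% of the time (uncorrected).

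The rarer the event, the larger the artefact, because more of the missing days are non-events.

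**Case C: the opposite pattern. True fall from 40% to 25%, missing 10% then 30%.**
- Week 1: 0.40 + 0.10 × 0.60 = 0.46
- Week 8: 0.25 + 0.30 × 0.75 = 0.475
- Apparent change: +1.5 points against a true −15. Here the fill works against the intervention, as the label says.

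**Dependence on q.** Keep the missing fractions of Case A. If every missing day is a drinking day (q = 1), the bias is zero. If 70% are, the bias is 0.30 × (0.10 − 0.25) = −4.5 points. At q = 40% it is the −9 points above.

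**The case against.** Several points on the other side stand.

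- **Hiding a benefit is not a breach of the label.** A reader might infer from Case C that the rule also fails by masking a true effect. That is what a conservative rule does. It attenuates the estimate, which matters for a pilot interested in effect sizes, but it does not contradict the SAP. Nor is all the lost power due to the fill: in Case C detection is about 45% with no missing data, about 28% using complete pairs with the same missingness, and about 2% after filling. The fair comparator is 28%.
- **The documents do not show that week 1 will have more missing data.** A reader might infer it because monitoring begins the day after the first session. The protocol's statement is only that "Participants will be instructed to call the interventionist if they have any technical difficulties throughout the course of the study", which does not place the trouble in week 1. Session 1 includes orientation and handouts, and app installation is checked beforehand. Participants who stop responding would add missing values late, which makes the fill conservative. The harmful pattern is possible, not predicted.
- **The scenario's own premise is that missing days are events.** If that is literally true, the bias vanishes. The label therefore rests on an assumption that cannot be checked from the data, and technical failure is a foreseen alternative cause.
- **The first scenario is reported alongside.** In Cases A and B, leaving values missing is unbiased, so the two results would visibly disagree. That gives some protection, but the plan does not say how to read a disagreement, and the label points the reader towards trusting the filled result.

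None of this makes the unconditional label correct.

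**Conclusion.** The point holds in limited form. The SAP attributes to the fill a property that it has only when m8(1 − q8) is at least m1(1 − q1). When week 1 carries more missing data and some missing days are non-events, the rule creates a false improvement: 9 points for drinking and 13.5 points for nonadherence under the assumed rates. The false-benefit rate is about 17% (11% with the exact test) for drinking, against a nominal 2.5%.

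These sizes depend on assumed event rates, missing fractions, correlation and pairing, and on missingness unrelated to outcome. The algebraic condition does not. When missingness rises over the 8 weeks, the direction of the label is right and the cost is attenuation.

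The consequence is a mislabelled sensitivity analysis in a pilot, not a failed main test. A reader might also infer that the main daily analysis must become a repeated-measures logistic model. That may be preferred on other grounds, but this defect does not require it.

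**What to change.** 1. Delete the description of the fill as conservative, or state the condition under which it is.
2. Keep the fill as one sensitivity scenario. Add one that is worst-case for benefit, with week-1 missing values set to non-drinking, negative or adherent and week-8 missing values set to drinking, positive or nonadherent. A tipping-point analysis would serve instead.
3. Report the missing fraction at week 1 and at week 8 beside each result.

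The cost is a few lines of SAP text and code. The downside is that the worst-case bound is wide when much is missing. In Case A it would run from 0.40 × 0.75 = 30% to 46%, a 16-point apparent worsening where nothing changed. It should be presented as a bound, not an estimate; a tipping-point analysis is easier to interpret in that situation.

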 - i. If patients cannot be reached, researchers will attempt to contact them three additional times (one day later, three days later, and one week later). If they cannot be contacted by the third attempt, they will be considered lost to follow-up and will not be contacted again.
13. After the participant completes the study, a retrospective chart review will be conducted to obtain viral load measurements (minimum of 2) from the participant during the time period beginning 3 months prior to their entry into the study and up to 6 months after their entry into the study.

3b. Waitlist-control group

1. After randomization and enrollment, the participant will complete the baseline assessment either at the time of enrollment, at home, or during a subsequent appointment within the next 30 days
2. The interventionist will call the participant after enrollment and do the following:
 - a. Introduce themselves to the patient
 - b. Describe the study timeline
 - c. Discuss follow-up contact times and encourage the participant to stay in contact
 - d. Remind participant of incentives they will receive for participating
 - e. Provide information about the baseline assessment (if the participant has not already completed it)
3. The interventionist will contact participants using their chosen method of communication after 4 weeks to maintain contact and ensure that no adverse events have occurred
4. At 7 weeks, the interventionist will contact participants to obtain their availability for the next week to schedule the first intervention content session based on the shared calendar
5. One day before the videoconferencing session, the researcher will contact the participant via the participant's chosen method of contact to remind them of their appointment
6. At 8 weeks, the patient will come into the clinic to begin the intervention.
7. The patient will be given a laptop to complete the initial assessment battery
8. If the participant is in need of a study phone, the VA coordinator will provide this phone, along with the breathalyzer, to the participant
9. The participant will begin the first intervention session, which will consist of the following content/tasks:
 - a. Introductions and orientation to the technology (smartphone and breathalyzer, stored at the clinic; tutorial handouts provided)

- b. Review of self-monitoring procedures and setting of “do not disturb” hours
 - c. Review of breathing awareness exercise

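### The pooled long-term analysis is an uncontrolled before-after change labelled as an intervention effect, and the SAP's time labels conflict with the protocol's use of baseline for the waitlist arm

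*Combined protocol and SAP*

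**What the plan says.** The last paragraph of the Statistical Analysis Plan states that "All participants will have received the intervention by the end of the 8 week (2-month) post-intervention period". To study long-term effects of the intervention, "participants from both the waitlist-control and intervention group will be combined into a single dataset", and a generalized linear model and a multiple linear regression are fitted to change from baseline for each outcome. The first of two follow-up points is given as "8 weeks (immediate post-intervention; T2 for intervention group and T3 for waitlist-control"). The label of the second point reads "16 weeks (2 months post-intervention; T3 for intervention group and T4 for waitlist-control"). The SAP justifies the change score this way: "The rationale for fitting the change from baseline is that this model removes the effect of baseline differences". It adds that "All statistical hypothesis tests will be conducted using the standard 5% significance level".

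The SAP does not say which assessment is the baseline in either arm. Under Data, Collection and record keeping, the protocol lists four batteries in both arms: baseline and weeks 8, 16 and 24. I call these T1 to T4 in order, which agrees with the SAP's labels.

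The waitlist arm has two batteries before treatment. In Step 3b, item 1, "the participant will complete the baseline assessment either at the time of enrollment, at home" or at an appointment within 30 days (T1). In items 6 and 7, "At 8 weeks, the patient will come into the clinic to begin the intervention" and completes a further battery before Session 1 (T2).

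**The concern.** There are two linked problems.

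**No comparator.** Every follow-up value in the pooled model is taken after treatment, and no untreated reference is specified. A change score removes differences between people at the start. It does not separate treatment from whatever else changes over time. Regression to the mean is a realistic part of that here, because entry requires at-risk drinking in the past month. The label and the 5% rule invite a significant change to be reported as a tested long-term effect.

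**Conflicting baseline for the waitlist.** An analyst who follows the protocol's use of the word baseline takes T1. One who follows the SAP's interval labels takes T2. They would compute different change scores for the same people, about half the pooled sample if allocation is equal.

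**Working it through.** The plan gives no figure to reproduce: there is no SD, correlation, expected change or power statement for this analysis.

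**Step 1: intervals, from the protocol schedule.** In the waitlist arm, Session 1 is at week 8, T3 at week 16 and T4 at week 24 (Step 3b, items 6, 13 and 15).

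| Waitlist starting value | To T3 | To T4 |
|---|---|---|
| T2 (week 8) | 16 − 8 = 8 weeks | 24 − 8 = 16 weeks |
| T1 (enrolment) | 16 − 0 = 16 weeks | 24 − 0 = 24 weeks |

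The SAP's labels are 8 and 16 weeks, so only T2 fits. The T1 intervals are maxima if weeks are counted from enrolment, because T1 may be completed up to 30 days later. Even then they are 112 − 30 = 82 days and 168 − 30 = 138 days, against the labelled 56 and 112.

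**Step 2: which way the text points.**
- Towards T2: the SAP's interval labels; the protocol's use of the same name, the initial battery, for the pre-Session-1 questionnaire in both arms (Step 3a, item 3; Step 3b, item 7); and the exclusion criteria, which time the viral load test from the start of intervention in each arm.
- Towards T1: the word baseline, used for the enrolment questionnaire in Step 3b, item 1, and in the control-group incentive list, and listed apart from week 8 under Collection and record keeping. The exclusion criteria also use baseline for the intervention arm only and name the 8-week point separately for the waitlist.

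**Step 3: illustration of size.** All inputs except N = 50 and the 5% level are assumptions: outcome SD 1, 25 per arm, no dropout, no treatment effect, correlation 0.6 between any two assessments, two-sided test of zero mean change at one time point.

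SD of change = √(2(1 − 0.6)) = 0.894. SE of the pooled mean = 0.894/√50 = 0.126. Pooled bias = average of the two arms' untreated falls. Rejection rates are from 200,000 simulated trials per cell.

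| Assumed untreated fall | Waitlist start | Arm falls (intervention, waitlist) | Pooled bias | Rejects |
|---|---|---|---|---|
| Linear, 0.1 SD per 8 weeks, immediately post | T1 | 0.1, 0.2 | 0.15 | 21% |
| | T2 | 0.1, 0.1 | 0.10 | 12% |
| Same, 2 months post | T1 | 0.2, 0.3 | 0.25 | 49% |
| | T2 | 0.2, 0.2 | 0.20 | 34% |
| 0.3 SD, complete by week 8 | T1 | 0.3, 0.3 | 0.30 | 64% |
| | T2 | 0.3, 0 | 0.15 | 21% |
| None | either | 0, 0 | 0 | 5% |

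For the early fall, correlations of 0.4 to 0.8 give 48–91% (T1) and 15–36% (T2). With 40 completers at correlation 0.6 the rates are 54% and 17%.

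If an arm term were tested instead, the early fall gives 5% with T1 and 21% with T2. The linear fall gives 6.7% with T1 and 5% with T2.

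**Step 4: precision of the only untreated trend.** The 95% half-width of the waitlist T1–T2 change is t(0.975, n − 1) × √(2(1 − 0.6)/n). For n = 25 this is 2.064 × √(0.8/25) = 0.37 SD (0.45 to 0.26 for correlations 0.4 to 0.8). For n = 20 it is 0.42 SD.

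**The case against.** The strongest reply is that the design and the SAP already deal with most of this. A waitlist trial loses its comparator once the waitlist is treated, and the SAP says openly that everyone will have been treated. The controlled evidence is the week-8 between-group comparison, and there the SAP says the study was not powered and looks only for preliminary evidence. No decision rule depends on the pooled model. All of that stands. But the caveat follows the week-8 analyses and is not repeated for the pooled models, which keep their effect label and fall under the 5% rule. Low power also does not excuse bias.

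Three stronger readings are tempting, and the documents do not support them:
- *The SAP leaves the waitlist baseline wholly open.* It does not. Its interval labels imply T2. What remains is a conflict with the protocol's wording.
- *The plan has a 64% false-positive rate.* The SAP names neither a test of zero mean change nor an arm-term test. The 64% comes from the shape of decline that most separates T1 from T2, and it assumes the same correlation over 8 and 16 weeks. A waitlist T1–T3 correlation of 0.5 or 0.4 would lower it to about 59% or 55%.
- *The trial has no controlled evidence.* The randomised week-8 comparison has an untreated arm and is untouched.

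It is also fair to say that T2 is not a cure. It lowers the bias in the pooled mean in both scenarios without removing it, and under an early fall it can create a spurious arm difference.

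**Conclusion.** The point holds and should be fixed before analysis. The pooled change cannot isolate a treatment effect under either choice of baseline, and the stated rationale for change scores does not address change over time. The waitlist baseline needs an explicit statement because the SAP's labels and the protocol's terms disagree.

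Confidence is high on the text. The size is not known from the documents: it depends on the assumed amount and shape of untreated change, the correlation, equal allocation and completeness. In the illustrations the bias in the pooled mean is 0.10 to 0.30 SD, and if there is no untreated change the error rate stays at 5%. The finding concerns a secondary analysis in a pilot of 50.

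**What to change.** Amend the SAP wording as follows.

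1. Define the waitlist pre-intervention value as the T2 battery, completed at week 8 before Session 1, for questionnaire outcomes. For viral load, which comes from chart review and is not part of the battery, use the last value before Session 1 in each arm.
2. Describe the pooled result as uncontrolled within-person change after the intervention, not as a tested intervention effect. The relabelling is what matters; a confidence interval in place of a test carries the same bias.
3. Show the waitlist T1–T2 change beside it as the only untreated trend. It is too imprecise to serve as a correction.
4. State that any arm term in the pooled model is not read as an effect.
5. Rest preliminary efficacy statements on the randomised week-8 comparison already planned.

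The cost is text only, with no new data or visits. There are two downsides. The pooled result can no longer be presented as a tested effect. And with T2 the starting value is the first questionnaire in the intervention arm but the second in the waitlist arm, so the arms differ in prior assessment; item 4 is needed for that reason.
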